10.1. Adverse Events

An AE is defined by ICH E6(R2) as any untoward medical occurrence in a patient or clinical investigation subject administered a pharmaceutical product regardless of its causal relationship to the study treatment.

An AE can therefore be any unfavorable and unintended sign (including an abnormal laboratory finding), symptom, or disease temporally associated with the use of medicinal (investigational) product. The occurrence of an AE may come to the attention of study personnel during study visits and interviews of a study recipient presenting for medical care, or upon review by a study monitor. All AEs, including solicited local (infusion site) and systemic (subjective and quantitative) reactions, will be captured on the appropriate data collection form and in the eCRF.

A treatment-emergent AE (TEAE) is defined as any event that does not present before exposure to study drug or any event already present that worsens in intensity or frequency after exposure.

Only TEAEs will be included in summary tables.

Adverse events will be coded by preferred term (PT) and system organ class (SOC) using MedDRA (version to be delineated in the CSR).

A subject may have more than 1 AE for an SOC or PT. A subject with 2 or more AEs within the same level of summarization will be counted only once in that summarization level. In addition to the summarization of subjects with AE at each level, the frequencies of AE occurrences will also be summarized at each level. Percentages will be based upon the number of subjects in the safety population for each treatment group.

All AEs will be presented in a data listing.

10.1.1. Incidence of Adverse Events

An overview of AEs will be presented by treatment and total, including number and percentage of subjects with any:

- Treatment-emergent AE
- Treatment-related TEAE
- Moderate TEAE

- Treatment-related moderate TEAE
- Severe TEAE
- Treatment-related severe TEAE
- Serious TEAE
- Treatment-related Serious TEAE
- Treatment-emergent AE leading to early discontinuation
- Death

All TEAEs will be presented in a summary table by treatment and total for each SOC and PT. Percentages will be calculated out of the number of subjects in the safety population.

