8.1.1.1 Adverse Events Grading

All AEs (laboratory and clinical symptoms) will be graded for severity and assessed for relationship to the IP (see definitions below). Adverse events characterized as intermittent require documentation of onset and duration of each episode. The start and stop date of each reported AE will be recorded on the appropriate data collection form and eCRF. Changes in the severity of an AE will be documented to allow an assessment of the duration of the event at each level of intensity.

Severity of Event: Adverse events will be assessed by the Investigator using a protocol-defined grading system (toxicity table included in Section 17.2). For events not included in the protocol-defined grading system, the following guidelines will be used to quantify severity:

- Mild (Grade 1): Events that are transient and may require only minimal or no treatment or therapeutic intervention and do not interfere with the subject's usual activities of daily living.
- Moderate (Grade 2): Events that are alleviated with additional specific therapeutic intervention. The event interferes with usual activities of daily living, causing discomfort but poses no significant or permanent risk of harm to the subject.
- Severe (Grade 3): Events interrupt usual activities of daily living, or significantly affects clinical status, or may require intensive therapeutic intervention. Severe events are usually incapacitating.

Relationship to Investigational Product: The assessment of the AE's relationship to the IP will be done by the licensed study physician indicated on Form FDA 1572 and the assessment will be part of the documentation process. Whether the AE is related or not, is not a factor in determining what is or is not reported in this study. If there is any doubt as to whether a clinical observation is an AE, the event should be reported.

In a clinical trial, the IP must always be suspect. The relationship to the IP will be assessed for AEs using the terms related or not related:

- Related There is a reasonable possibility that the IP caused the AE. Reasonable possibility means that there is evidence to suggest a causal relationship between the IP and the AE.
- Not Related There is not a reasonable possibility that the administration of the IP caused the event.

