8.2 Specification of Safety Parameters

Safety will be assessed by the frequency and severity of:

- Occurrence of SAEs from the administration of AV-1 to final follow-up visit on Day 120 (±5).
- Occurrence of unsolicited AEs from the administration of AV-1 to the final follow-up visit on Day 120 (±5).
- Occurrence of solicited AEs from the administration of AV-1 to Day 8.

- Occurrence of changes from baseline in physical examination, vital sign measurements, and clinical safety laboratory values from the administration of AV-1 to the final follow-up visit on Day 120 (±5).
- Occurrence of changes from baseline in ECG parameters in the 48 hours after starting the AV-1 infusion and at Days 8 (+2), 43 (\pm 3), 85 (\pm 5), and 120 (\pm 5).

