8.2.1 Solicited and Unsolicited Events

Solicited events are AEs that are common and known to occur following administration of the IP. Solicited events are defined in Table 17-1.

Unsolicited events are any other AEs that occur following administration of the IP.

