10.1.3. Severity of Adverse Event

All AEs (laboratory and clinical symptoms) will be graded for severity. The severity will be classified as mild, moderate, or severe using the following criteria:

- Mild (Grade 1): Events that are transient and may require only minimal or no treatment or therapeutic intervention and do not interfere with the subject's usual activities of daily living.
- Moderate (Grade 2): Events that are alleviated with additional specific therapeutic intervention. The event interferes with usual activities of daily living, causing discomfort but poses no significant or permanent risk of harm to the subject.
- Severe (Grade 3): Events interrupt usual activities of daily living, or significantly affects clinical status, or may require intensive therapeutic intervention. Severe events are usually incapacitating.

All TEAEs will be summarized for each treatment group and total by maximum severity. If the severity information is missing, the AE will be considered severe in the summary but will be presented as missing in the data listings.

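### Solicited adverse events to Day 8 are a named safety parameter that no planned table reports, and SAP 10.1.3 states the fallback severity criteria as if they covered every event

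*SAP*

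**What the plan says.** **Parameters.** Protocol 8.2 opens with "Safety will be assessed by the frequency and severity of" and then lists several items. One is "Occurrence of solicited AEs from the administration of AV-1 to Day 8". Unsolicited events, followed to the final visit on Day 120, are a different item. Protocol 8.2.1 adds: "Solicited events are defined in Table 17-1".

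**Grading.** Protocol 8.1.1.1 says "Adverse events will be assessed by the Investigator using a protocol-defined grading system", meaning the toxicity tables in Section 17.2. The generic mild, moderate and severe wording comes second: "For events not included in the protocol-defined grading system, the following guidelines will be used to quantify severity".

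**Planned summaries.** Protocol 10.4.5 plans treatment-emergent events by treatment and overall, by severity and by relationship. The SAP follows this with an overview table, a table by system organ class and preferred term (SAP 10.1.1: "All TEAEs will be presented in a summary table by treatment and total for each SOC and PT"), a table by relationship and a table by maximum severity. SAP 10.1 mentions solicited reactions only as data to be captured, and the schedule in SAP Appendix 1 repeats the two collection windows. On severity, SAP 10.1.3 speaks of all adverse events and says "The severity will be classified as mild, moderate, or severe using the following criteria"; the generic wording follows.

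**The concern.** Solicited and unsolicited events differ in two ways: how they are ascertained, and how long they are collected. A table that pools them over 120 days answers neither question cleanly. A reader who wants to know how many subjects at each dose had a solicited reaction in the first week, and how severe it was, will not find that figure in any planned adverse event table.

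The severity wording is a separate inconsistency. If the clinical study report describes grades by the SAP text, it will describe a different scale from the one that the protocol tells the investigator to use for the events in the toxicity tables. Those are the solicited events.

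**Working it through.** The documents give no adverse event rates and no figure to reproduce for this point. The check is mainly a comparison of texts, followed by an illustration of scale.

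**1. Parameter against planned output**

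| Item in Protocol 8.2 | Window | Protocol 10.4.5 | SAP 10.1.1 to 10.1.3 |
|---|---|---|---|
| Solicited events, frequency | to Day 8 | no separate summary | no solicited row, no Day 8 cut |
| Solicited events, severity | to Day 8 | no separate summary | only within all treatment-emergent events |
| Unsolicited events | to Day 120 | no separate summary | only within all treatment-emergent events |

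SAP 11 lists one departure from the protocol, the definition of the safety population.

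**2. Where the two severity scales can disagree**

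| Event | Table 17-1 | Generic criteria |
|---|---|---|
| Erythema 5.1 to 10 cm, transient, activity unaffected | Grade 2 | fits Grade 1 |
| Headache treated with a narcotic pain reliever | Grade 3 | can fit Grade 2 (relieved by a specific treatment) |
| Dyspnea that needs treatment | Grade 3 | can fit Grade 2 (same reason) |

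SAP Appendix 3 reprints Tables 17-1 to 17-4. The SAP text refers to that appendix only in 10.2, 10.3 and 10.4, for laboratory tests, vital signs and ECG. Section 10.1.3 does not refer to it.

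**3. Scale of the pooling effect (assumed rates)**

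The solicited window is 8/120 = 6.7% of the follow-up.

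*One symptom.* Assume a constant background risk q per 28 days, and an infusion that adds an independent acute risk of 20% by Day 8. Placebo incidence by day t is p(t) = 1 − (1 − q)^(t/28). The difference, AV-1 minus placebo, is 0.20 × (1 − p(t)).

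| q | p(8) | p(120) | Difference by Day 8 | Difference over 120 days |
|---|---|---|---|---|
| 2% | 0.6% | 8.3% | 19.9 points | 18.3 points |
| 5% | 1.5% | 19.7% | 19.7 points | 16.1 points |
| 10% | 3.0% | 36.3% | 19.4 points | 12.7 points |

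The share of background first events after Day 8 is 1 − p(8)/p(120), or 92% to 93%. A 120-day row for a preferred term is therefore not a Day 8 solicited rate.

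*The coarsest row, any treatment-emergent event.* Assume solicited incidence s of 10% on placebo and 30% on AV-1, and an independent background b for any other event. The row shows 1 − (1 − b)(1 − s).

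- b = 30%: 37% against 51%, a difference of 14 points
- b = 50%: 55% against 65%, a difference of 10 points
- b = 70%: 73% against 79%, a difference of 6 points

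**4. Precision.** The groups are 6 per dose and 5 × 2 = 10 pooled placebo. One subject in 6 is 16.7 points. The two-sided 95% exact upper limit, 1 − 0.025^(1/n), is 45.9% for 0/6 and 30.8% for 0/10.

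**The case against.** **The SAP follows the protocol's own analysis section.** Protocol 10.4.5 plans no solicited table, and the primary endpoint in 3.3.1 does not split adverse events either. This stands. The gap begins within the protocol, between 8.2 and 10.4.5. It does not excuse the SAP, because Protocol 10.4 and 10.4.2 leave the analysis detail to it and 8.2 already says what is to be assessed.

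**A reader might infer that the SAP replaces Table 17-1 grading.** The documents do not support that. The investigator assigns grades under Protocol 8.1.1.1, the tables are reprinted in SAP Appendix 3, and SAP 11 declares no change. Section 10.1.3 may be no more than a shortened copy of the protocol text. What stands is an unreconciled wording conflict.

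**A reader might infer that the solicited parameter can never be estimated.** That is also too strong. All events are listed, symptoms can be read by preferred term, and QTcF and PR (both rows of Table 17-1) are graded by Appendix 3 and tabulated by visit. A Day 8 summary is unplanned, not impossible. The table by relationship is not a full substitute, because relatedness is the investigator's judgment.

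**The dilution is small against the noise.** This largely stands. The losses of 6, 10 and 14 points in the coarsest row are each less than one subject in a dose group of 6. No safety hypothesis is tested, and dose escalation rests on blinded review of data through Day 8, not on these final tables.

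**The split cannot be programmed from Table 17-1 as it stands.** Correct. Its last row is a catch-all for any illness or clinical event, so on a literal reading nearly every clinical event would be solicited. The solicited terms must be limited first.

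**Conclusion.** The point holds in a limited form and is of low priority. Two things follow from the text without any assumption. A safety parameter named in Protocol 8.2 has no planned summary in Protocol 10.4.5 or the SAP. SAP 10.1.3 omits the restriction in Protocol 8.1.1.1, and the two scales can then assign different grades to the same event.

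The dilution figures are only an illustration. They rest on assumed rates, a constant background risk and independence. At symptom level they suggest a loss of about 1.6 to 6.7 points (19.9 − 18.3 and 19.4 − 12.7) from a difference of about 20.

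It would be tempting to argue that reactions soon after infusion are the most likely effect of AV-1, which would make the omission more serious. The documents do not say so. Protocol 2.2.2 anticipates no drug-related toxicity, and 2.3.1 allows for both immediate and delayed events. The case for the change rests on reporting what the protocol names, on one stated scale.

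Table shells and case report forms are not in the documents. A shell may already contain the split. Deriving it later depends on the database holding a solicited flag and onset dates.

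**What to change.** In SAP 10.1:

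- Add a table of solicited adverse events from the start of infusion to Day 8, by dose level and pooled placebo, with a row for any solicited event and one for each term, by maximum Table 17-1 grade. Limit it to the specific terms collected as solicited, list them, and exclude the catch-all illness row.
- Add a table of unsolicited treatment-emergent events to Day 120 by the same groups. Say where a listed solicited term with onset after Day 8 is counted.
- Optionally, add a row for infusion-related reactions by Table 17-4 grade. Protocol 8.2 and 10.4.5 name no such summary, so this is an extra.

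In SAP 10.1.3, restore the order in Protocol 8.1.1.1: the Appendix 3 tables apply first, and the generic criteria apply only to events not specifically named in them.

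The existing tables, the conduct of the study and the sample size are unchanged. The data are already due to be collected, and the cost is SAP wording and a little more programming.

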10.1.2. Relationship of Adverse Events to Study Drug

The relationship or association of the study drug in causing or contributing to the AE will be characterized by the investigator as "Related" or "Not Related".

All TEAEs will be presented in a summary table for each treatment group and total by relationship to study drug. If a subject has 2 or more TEAEs in the same SOC (or with the same PT) with a different relationship to study drug, then a "Related" event will be used for that subject. If the relationship information is missing, the AE will be considered related in the summary but will be presented as missing in the data listings.

10.1.3. Severity of Adverse Event

All AEs (laboratory and clinical symptoms) will be graded for severity. The severity will be classified as mild, moderate, or severe using the following criteria:

- Mild (Grade 1): Events that are transient and may require only minimal or no treatment or therapeutic intervention and do not interfere with the subject's usual activities of daily living.
- Moderate (Grade 2): Events that are alleviated with additional specific therapeutic intervention. The event interferes with usual activities of daily living, causing discomfort but poses no significant or permanent risk of harm to the subject.
- Severe (Grade 3): Events interrupt usual activities of daily living, or significantly affects clinical status, or may require intensive therapeutic intervention. Severe events are usually incapacitating.

All TEAEs will be summarized for each treatment group and total by maximum severity. If the severity information is missing, the AE will be considered severe in the summary but will be presented as missing in the data listings.

10.1.4. Serious Adverse Events

An AE or suspected adverse reaction is considered an SAE/suspected unexpected serious adverse reaction if, in the view of either the investigator or sponsor, it results in any of the following outcomes:

- Death
- Life-threatening AE
- Inpatient hospitalization or prolongation of existing hospitalization
- A persistent or significant incapacity or substantial disruption of the ability to conduct normal life functions, or
- A congenital anomaly or birth defect

Important medical events that may not result in death, be life threatening, or require hospitalization may be considered serious when, based upon appropriate medical judgment, they may jeopardize the subject and may require medical or surgical intervention to prevent one of the outcomes listed in this definition. Examples of such medical events include allergic bronchospasm requiring intensive treatment in an emergency room or at home, blood dyscrasias or convulsions that do not result in inpatient hospitalization, or the development of drug dependency or drug abuse.

All SAEs will be presented in a data listing.

10.1.5. Adverse Events Leading to Study Drug Discontinuation

An AE where the answer to "What action was taken with study treatment?" is "Drug Withdrawn" will be considered an AE leading to study drug discontinuation.

All AEs leading to study drug discontinuation will be presented in a data listing.

10.2. Clinical Laboratory Evaluations

Clinical laboratory testing will occur at Screening, Check-in, predose (within 60 minutes) and 48 hours after the start of the IP infusion on Day 1; and on Days 8, 15, 22, 43, 85, and 120. A complete list of assessments is provided in Appendix 2.

Actual results and changes from baseline values for hematology, coagulation, serum chemistry, and urinalysis tests will be summarized by visit and treatment for subjects in the safety population. The key parameters will be evaluated based on toxicity grading scale in Appendix 3, and the toxicity grades will be summarized in tables for subjects in safety population.

Shift from baseline in hematology, coagulation, serum chemistry, and urinalysis test results relative to the reference range will be summarized by visit and treatment using the frequency count and percentage of subjects in each category.

Serology, urine drug screen, Flavivirus screening, and pregnancy test data will not be summarized.

All laboratory data will be presented in data listings.

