3.2.3. Immunogenicity Endpoints

Incidence of anti-AV-1 antibodies as measured by the proportion of subjects with detectable anti-AV-1 antibody signal in serum, including treatment-emergent anti-AV-antibodies, using an electrochemiluminescence (ECL) enzyme-linked immunosorbent assay (ELISA).

4. General Statistical Considerations

All data collected will be presented in data listings. Data from subjects excluded from an analysis population will be presented in the data listings but not included in the calculation of summary statistics.

For categorical variables, frequencies and percentages will be presented. Continuous variables will be summarized using descriptive statistics (number of subjects, mean, median, standard deviation [SD], minimum, and maximum).

Unless specified otherwise, baseline will be defined as the last non-missing assessment prior to the study drug administration. Unscheduled visits will be used in determining baseline.

Unless otherwise indicated, outputs which are summarized by treatment will be summarized for each dose level for subjects on active study drug; subjects who receive placebo will be pooled into a single group.

The study day of dosing will be considered as Day 1. Study day will be calculated relative to the first dose date as follows:

- If assessment date is on or after the first dose of study drug administration, then Study Day = Assessment Date - Dose Date + 1
- Otherwise, Study Day = Assessment Date Dose Date

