10.3. Vital Sign Measurements and Weight

Vital signs will be measured at Screening and Check-in; within 60 minutes prior to start of the IP infusion; at 0.5, 1 (± 10 minutes), 2, 4, 8, 24, and 48 hours after the start of the IP infusion; and on Days 5, 8, 15, 22, 43, 85, and 120 (or ET). Vital signs will include systolic and diastolic blood pressure, heart rate, and oral body temperature. The subject will have rested comfortably in a seated or supine position for at least 5 minutes before all measurements are taken.

Actual values and changes from baseline for vital sign data will be summarized by visit and treatment for subjects in the safety population. Changes from baseline to each scheduled post-baseline visit will be presented. Only systolic and diastolic blood pressure, heart rate, respiratory rate and temperature will be included in the summary tables. These key parameters will also be graded based on toxicity grading scale in Appendix 3, and the grades will be summarized in a table by visit and treatment for subjects in the safety population.

All vital sign, height, and weight measurements will be presented in a data listing.

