10.4. Electrocardiograms

Single 12-lead ECG recordings will be made at Screening, within 60 minutes prior to the start of the IP infusion; at 1 (\pm 10 minutes), 2, 4, 8, and 24 hours after the start of the IP infusion; and on Days 8, 43, 85, and 120 (or ET). Electrocardiograms will be recorded after the subject has been in the supine position for at least 10 minutes. A single repeat measurement is permitted at Screening for eligibility determination. Measurements of the following intervals will be reported: RR interval, PR interval, QRS width, QT interval, and QTcF. Assessments should include comments on whether the tracings are normal or abnormal; rhythm; presence of arrhythmia or conduction defects; morphology; any evidence of myocardial infarction; or ST-segment, T-wave, and U-wave abnormalities.

Actual values and changes from baseline for numeric ECG data will be summarized by visit and treatment for subjects in the safety population. Key parameters including QTcF and PR interval will be graded based on toxicity grading scale in Appendix 3, and the

toxicity grades will be summarized in a table by visit and treatment for subjects in the safety population.

Shift from baseline in interpretation of ECG results will be summarized by visit and treatment using the frequency count and percentage of subjects in each category.

All ECG data will be presented in a data listing.

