Appendix 3 Toxicity Tables

Cardiovascular	Mild (Grade 1)	Moderate (Grade 2)	Severe (Grade 3)
Arrhythmia	N/A	Asymptomatic; transient signs; no medical intervention required	Recurrent or persistent symptoms; medical intervention required
Hemorrhage, Blood Loss [*]	Estimated blood loss is <100 mL	Estimated blood loss is ≥100 mL; no transfusion required	Transfusion required
QTc (Fridericia's correction)	Asymptomatic, QT interval 450 to 479 msec (male) and 460 to 479 msec (female) OR increase in interval <30 msec above baseline	Asymptomatic, QTc interval 480 to 499 msec OR increase in interval 30 to 50 msec above baseline	Asymptomatic, QTc interval ≥500 msec OR increase in interval ≥60 msec above baseline
PR Interval	PR interval 0.21 to	PR interval >0.25 sec	Type II 2 nd degree AV block
(prolonged)	0.25 sec		OR ventricular pause >3 sec
Respiratory	Mild (Grade 1)	Moderate (Grade 2)	Severe (Grade 3)
Cough	treatment	Persistent	activities
Bronchospasm, Acute	Transient; no treatment; forced expiratory volume 71 to 80% of predicted peak flow	Requires medical intervention; normalizes with bronchodilator; forced expiratory volume 60 to 70% of predicted peak flow	No normalization with bronchodilator; forced expiratory volume <60% of predicted peak flow
Dyspnea	Does not interfere with usual and social activities	Interferes with usual and social activities; no treatment	Prevents daily and usual social activity OR requires treatment
Gastrointestinal	Mild (Grade 1)	Moderate (Grade 2)	Severe (Grade 3)
Nausea	No interference with activity	Some interference with activity	Prevents daily activity
Vomiting	No interference with activity OR 1 to 2 episodes/24 hours	Some interference with activity OR >2 episodes/24 hours	Prevents daily activity OR requires IV hydration OR requires medical intervention
Diarrhea	2 to 3 loose or watery stools OR <400 grams/24 hours	4 to 5 loose or watery stools OR 400 to 800 grams/24 hours	6 or more loose or watery stools OR >800 grams/24 hours OR requires IV hydration OR requires medical intervention
Local Reactions	Mild (Grade 1)	Moderate (Grade 2)	Severe (Grade 3)
Pain	Does not interfere with activity	Repeated use of non-narcotic pain reliever > 24 hours OR interferes with activity	Any use of narcotic pain reliever OR prevents daily activity

Table 17-1	Toxicity Grading Scales for Clinical Adverse Events and Reactions
------------	--

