Laboratory Tests	Mild (Grade 1)	Moderate (Grade 2)	Severe (Grade 3)
Liver Function Tests – ALT increase by factor	1.1-2.5 imes ULN	2.6-5.0 imes ULN	>5.0 × ULN
Liver Function Tests – AST increase by factor	1.1 - 2.5 imes ULN	2.6-5.0 imes ULN	>5.0 × ULN
Albumin – Hypoalbuminemia g/dL	2.8 - 3.1	2.5 - 2.7	<2.5
Alkaline Phosphatase – ALP increase by factor	1.1 - 2.0 imes ULN	>2.0 - 3.0 × ULN	>3.0 × ULN
Anion Gap* – mEq/L	N/A	N/A	N/A
Bilirubin (total) – mg/dL	$1.1 - < 1.6 \times ULN$	$1.6 - < 2.6 \times ULN$	\geq 2.6 × ULN
Blood Urea Nitrogen mg/dL	27 - 30	31 - 35	> 35
Calcium – Hypocalcemia mg/dL	8.0 - 8.4	7.5 – 7.9	7.0 - 7.4
Calcium – Hypercalcemia mg/dL	10.5 - 11.0	11.1 – 11.5	11.6 - 12.0
Creatinine – mg/dL	$1.2 - 1.3 \times ULN$	>1.3 – 1.8 × ULN	>1.8 × ULN
Glucose (fasted) – Hypoglycemia mg/dL	50 - 54	40 - 49	30 - 39
Glucose (fasted) – Hyperglycemia Fasting – mg/dL	117 – 127	128 – 142	>143
Potassium – Hypokalemia mEq/L	3.3 – 3.4	3.1 - 3.2	2.9-3.0
Potassium – Hyperkalemia mEg/L	5.1 - 5.2	5.3 - 5.4	5.5 - 5.6
Sodium – Hyponatremia	129 – 131	127 - 128	122 - 126
Sodium – Hypernatremia mEq/L	146 – 147	148 – 149	150 - 152
Hematology	Hematology		
WBC increase - cell/mm ³	9.800 - 14.000	14.001 - 19.000	19.001 - 24.000
WBC decrease - cell/mm ³	2.000 - 3.099	1.000 - 1.999	500 - 999
Absolute Neutrophil Count - cell/mm ³	1,000 – 1.499	500 - 999	0 - 499
Hemoglobin Decrease (female) - gm/dL	9.7 - 10.7	8.2 - 9.6	6.7 - 8.1
Hemoglobin Decrease (male) - gm/dL	11.7 – 12.7	9.76 - 11.6	7.6 - 9.6
Platelets Decrease - cell/mm ³	125.000 - 139.000	100.000 - 124.000	<100.000
Coagulation	- ,		
Prothrombin Time – increase by factor	>1.0 – 1.2 × ULN	$1.2 - 1.4 \times ULN$	>1.4 × ULN
Activated Partial thromboplastin time – increase by factor	>1.0 - 1.2 × ULN	1.2 – 1.4 × ULN	>1.4 × ULN

Table 17-3 Laboratory Toxicity Grading

Laboratory Tests	Mild (Grade 1)	Moderate (Grade 2)	Severe (Grade 3)
Urine			
Blood**	1+	2+	>2+
Glucose	1+	2+	>2+
Protein	1+	2+	>2+

Abbreviations: ALP, alkaline phosphatase; ALT, alanine transferase; AST, aspartate aminotransferase; ULN, upper limit of the normal range, WBC, white blood cell.

*Only values above the ULN and below the LLN are considered abnormal.

**For females: In case of menstruation, screening urinalysis must be postponed, but a result should be available prior to Day 1. Hematuria is acceptable for females in menses for the purposes of evaluating study halting criteria and dose escalation.

Source: DHHS 2007.

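### The toxicity bands that the SAP tabulates leave some severe and in-between values ungraded and, read literally, make any QTcF increase below 30 msec Grade 1

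*SAP*

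**What the plan says.** The SAP grades three kinds of safety data from one appendix and tabulates the grades.

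- Laboratory tests (SAP 10.2): "The key parameters will be evaluated based on toxicity grading scale in" Appendix 3.
- Vital signs (SAP 10.3): "These key parameters will also be graded based on toxicity grading scale in" Appendix 3. Temperature is among the parameters named.
- ECGs (SAP 10.4): "Key parameters including QTcF and PR interval will be graded based on toxicity grading scale in" Appendix 3.

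The change part of the QTcF scale in Table 17-1 has three bands. Grade 1 is "increase in interval <30 msec above baseline", Grade 2 is "increase in interval 30 to 50 msec above baseline", and Grade 3 is an increase of 60 msec or more. Each is joined by OR to a band on the absolute interval. Under SAP Section 4, "baseline will be defined as the last non-missing assessment prior to the study drug administration".

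There is no Grade 4. SAP 10.2 to 10.4 do not say what happens to a value beyond the last band or between two bands. Protocol Section 17.2 prints the same bands.

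**The concern.** A programmer has to turn these bands into code. As printed, they fail in two ways. Some values get no grade although a milder value does, so a grade table can understate the most extreme results. In the other direction, the lowest QTcF change band has no lower limit, so a rise of 1 msec counts as toxicity and ordinary variation fills the table.

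Laboratory, vital-sign and ECG results are all primary safety endpoints (SAP 3.2.1). How they are graded should be fixed in the plan, not left to whoever writes the program. The same tables also sit behind protocol 8.5, which calls for an immediate repeat of findings that meet Grade 3 criteria. Read literally, a potassium of 5.7 does not meet them.

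**Working it through.** The documents give no figure of their own on this point, so the check applies the printed bands literally.

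**1. Closed Grade 3 bands.** Table 17-2 has 7 scales (fever in °C and °F counted once) and Table 17-3 has 27, so 34 in all. Sorted by how Grade 3 ends: 12 close at a limit that can be exceeded, 20 are open-ended, neutrophils end at 0, and anion gap has no grades (12 + 20 + 1 + 1 = 34). Two of the 12 are calcium low and high, which footnote (a) of SAP Appendix 2 restricts to Screening and Check-in. That leaves 12 − 2 = 10 measured after dosing.

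| Scale | Grade 3 as printed | First value with no grade |
|---|---|---|
| Fever, °C | 39.0 to 40 | 40.1 |
| Glucose low, mg/dL | 30–39 | 29 |
| Potassium low, mEq/L | 2.9–3.0 | 2.8 |
| Potassium high, mEq/L | 5.5–5.6 | 5.7 |
| Sodium low, mEq/L | 122–126 | 121 |
| Sodium high, mEq/L | 150–152 | 153 |
| WBC low, /mm³ | 500–999 | 499 |
| WBC high, /mm³ | 19,001–24,000 | 24,001 |
| Hemoglobin female, g/dL | 6.7–8.1 | 6.6 |
| Hemoglobin male, g/dL | 7.6–9.6 | 7.5 |

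The last column takes the next value at the precision printed, and for temperature at one decimal. Fever is named for tabulation in SAP 10.3. The other nine are laboratory rows and count only if they are among the key parameters of SAP 10.2.

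**2. QTcF change bands.** Take a baseline of 380 msec, so that every absolute value below stays under the absolute bands (450 msec for men, 460 for women):

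- +20 (400 msec): Grade 1
- +40 (420 msec): Grade 2
- +55 (435 msec): no grade
- +60 (440 msec): Grade 3

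Now hold the absolute value at 460 msec. An increase of 50 is Grade 2, 51 to 59 drops to Grade 1 through the absolute band, and 60 is Grade 3. The scale is not monotonic.

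**3. How often the band below 30 msec applies.** The post-dose ECGs are at 1 hour and at "2, 4, 8, and 24 hours after the start of the IP infusion; and on Days 8, 43, 85, and 120", that is 5 + 4 = 9, compared with one predose baseline. With no drug effect and 10 exchangeable readings, the baseline is the largest with probability 1/10. So P(at least one increase) = 1 − 1/10 = 0.9 before ties, or 40 × 0.9 = 36 of 40 subjects. Nearly all of these would carry Grade 1 or higher.

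For single readings an SD of the change is needed, and the documents give none. Assume a normal change with mean 0, recorded in whole msec, and an SD of 8 to 20 msec:

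| SD (msec) | P(increase 1–29) | P(increase 51–59) |
|---|---|---|
| 8 | 0.475 | 0.000 |
| 10 | 0.478 | 0.000 |
| 12 | 0.476 | 0.00001 |
| 15 | 0.462 | 0.0003 |
| 20 | 0.420 | 0.0043 |

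At each time point that is 6 × 0.420 = 2.5 to 6 × 0.478 = 2.9 subjects of 6 in a dose group, and 4.2 to 4.8 of the 10 pooled placebo subjects. Over 40 × 9 = 360 readings, increases of 51 to 59 msec number from 0 to 360 × 0.0043 = 1.5.

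**4. Other interior faults.** Fasting glucose runs 128–142 and then >143, so exactly 143 has no grade. Male hemoglobin runs 7.6–9.6 and then 9.76–11.6, so 9.7 has none. Neutrophil Grade 1 is printed as 1,000 to 1.499, which cannot be a band as it stands.

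**The case against.** The strongest reply is that little turns on this. Any programmer would put potassium 5.7 in Grade 3, the hemoglobin and neutrophil limits are plainly typographical, and values past Grade 3 should be rare in screened healthy volunteers. With no drug effect the QTcF noise falls equally on active and placebo. Most of this stands and is why the point is minor. But common sense does not settle QTcF +55 or +5, and there the programmer's choice changes the table.

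A second reply is that fallbacks exist: SAP 10.1.3 counts an AE of missing severity as severe, and protocol 8.1.1.1 gives general definitions for events outside the grading system. Both concern AEs, not the laboratory, vital-sign and ECG grade tables.

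Some stronger readings are tempting, and the documents do not support them:

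- **That 12 of 34 scales are faulty where it matters.** Two are calcium, tested only before dosing, and nine of the other ten depend on the key parameters.
- **That halting rules fail or severe results escape notice.** Protocol 8.6.3 prints its own QTcF thresholds, so the 51–59 msec gap does not touch that criterion. Clinically significant results go on the AE page (7.1) and to the sponsor before escalation (8.2.2), laboratory results are reviewed within 24 hours (8.5), and one IP-related SAE stops dosing (8.6.3).
- **That the fault is confined to the grade tables.** Protocol 8.1.1.1 and 8.5 use the same Section 17.2 tables, so that is not shown either.
- **That ALT/AST between 2.5 and 2.6 × ULN and PT/aPTT at 1.2 × ULN add to the case.** The first gap vanishes when the multiple is rounded to the printed decimal, and PT/aPTT are measured only before dosing.
- **That the unlisted key parameters are an error.** That is a request for detail.

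**Conclusion.** The point holds as a minor one. The printed rule itself misgrades values, which is more than missing detail. Ten scales measured after dosing have an exceedable Grade 3 limit, QTcF increases of 51 to 59 msec have no change-based grade, glucose 143 and male hemoglobin 9.7 fall between bands, and one neutrophil limit is misprinted. These follow from the tables and need no assumption beyond reporting at the printed precision (one decimal for temperature).

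Only the QTcF band below 30 msec touches ordinary data. The figure of about 9 in 10 subjects rests on no drug effect and exchangeable readings, before ties; time-of-day effects would change it. The single-reading figures rest on the assumed SD range. The result would be an uninformative QTcF grade table, not a biased comparison. Actual values and changes from baseline are summarized, laboratory shift tables are planned, and all data are listed. No hypothesis is formally tested on a grade (protocol 10.1).

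**What to change.** In SAP Appendix 3, state for tabulation only:

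1. A value beyond the outer limit of Grade 3 counts as Grade 3, as it already does on the 20 open-ended scales.
2. A value past one band but short of the next keeps the grade of the band it has passed.

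Under these rules potassium 5.7 and temperature 40.1 °C are tabulated as Grade 3, and QTcF +55, glucose 143 and male hemoglobin 9.7 as Grade 2.

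The sponsor should also:

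- state how QTcF increases below 30 msec are tabulated, for example by showing the absolute and change parts of the scale separately;
- correct the printed neutrophil and male hemoglobin limits;
- reconcile protocol Tables 17-1 to 17-3 with the Grade 3 references in protocol 8.5, 8.6.1 and 8.6.3.

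No clinical threshold or rule is proposed here. The cost is a few sentences in the SAP and a check of the protocol tables, with no new data. The downside is that a few more values may be counted as Grade 3.
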